## 1. SYNOPSIS

NAME OF SPONSOR: Gan & Lee Pharmaceuticals USA	PROTOCOL No.: GL-GLAT1-3001
NAME OF STUDY TREATMENT: Gan & Lee Insulin Glargine Injection	
TITLE OF STUDY: An Open-label, Randomized, Multicenter, Phase 3 Study to Compare the Immunogenicity, Efficacy, and Safety of Gan & Lee Pharmaceuticals Insulin Glargine Injection to Lantus® (Insulin Glargine Injection) in Adult Subjects with Type 1 Diabetes Mellitus	
STUDY CENTERS: Approximately 100 sites are planned in the United States and Europe	
STUDY PERIOD: Subjects randomized to the Gan & Lee Insulin Glargine Injection group or the Lantus® group will receive treatment for 26 weeks.	PHASE OF DEVELOPMENT: Phase 3
PLANNED STUDY DATES: The study started in 2017 and is expected to end in 2019	
OBJECTIVES:	
Primary Objective:	

To evaluate equivalence of Gan & Lee Insulin Glargine Injection and Lantus® in terms of immunogenicity

	
Secondary Objectives:	

Immunogenicity: To evaluate the percentage of subjects with negative anti-insulin antibodies (AIAs) at baseline who develop confirmed positive AIA up to visit Week 26, the percentage of subjects with at least a 4-fold increase in titers compared to baseline value, mean change from baseline in AIA titers between treatment groups, the percentage of subjects with confirmed positive AIA who develop any anti-insulin neutralizing antibodies up to visit Week 26, and percentage of subjects who develop confirmed positive AIA up to visit Week 26 of Gan & Lee Insulin Glargine Injection in comparison with that of Lantus®.

Safety: To evaluate the safety of Gan & Lee Insulin Glargine Injection in comparison with that of Lantus®.

Efficacy: To evaluate the efficacy of Gan & Lee Insulin Glargine Injection in comparison with that of Lantus®.

	
Exploratory Objectives:	

To investigate the retrospective hypoglycemic rate and the time in hypoglycemia and hyperglycemia using continuous glucose monitoring (CGM) data

To examine the relationship between the plasma concentrations of insulin glargine, M1, and M2, and immunogenic response

	

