### 11.3 Adverse Events of Special Interest

An adverse event of special interest is a noteworthy serious or nonserious event that a sponsor may want to carefully monitor because it might be a potential precursor or prodrome for a more serious condition in susceptible individuals. In this study, hypoglycemia will be monitored as an adverse event of special interest. When an adverse event of hypoglycemia is entered into the electronic data capture system, the system will prompt the user to provide additional information.

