### **12.2 Sample Size Estimation**

Enrollment is planned for 550 subjects overall (275 subjects per treatment group). The primary analysis for immunogenicity will be an equivalence test using the 2 one-sided tests (TOST) approach with  $\alpha=0.05$ . This sample size was chosen to achieve over 80% power on the equivalence test of proportion of subjects under the margins dependent on the observed treatment-induced AIA rate. For example, a sample size of 550 will provide approximately 85% power on the equivalence test of proportion of subjects with treatment-induced AIA using an event rate of 30% and a margin of 12% ([Table 4](#)). The treatment-induced AIA is defined as newly confirmed positive AIA development or important (at least a 4-fold) increase in AIA titers, after baseline and up to visit Week 26. For this sample size of 550, no drop outs are considered in the calculation. Subjects will be encouraged to come back for assessments even if they have discontinued treatment early.

The similarity margin, based on the actual observed event rate for the intended reference product, will be used for final analysis after database lock as summarized in [Table 4](#). Linear interpolation will be used for values between AIA rates in the table.

**Table 4: Similarity Margins for Actual Observed Event Rate of Proposed Biosimilar to Insulin Glargine for Various Immunogenicity Event Rates**

Treatment-induced AIA Rate for the Reference Product	Margin	Power
10%	7.9%	83%
15%	9.3%	83%
20%	10.5%	84%
25%	11.3%	84%
30%	12.0%	85%
35%	12.5%	85%
40%	12.8%	85%
45%	13.0%	85%
50%	13.1%	85%
55%	13.0%	85%
60%	12.8%	85%
65%	12.5%	85%
70%	12.0%	85%
75%	11.3%	84%
80%	10.5%	84%
85%	9.3%	83%
90%	7.9%	83%

AIA = anti-insulin antibodies.

Sample size calculations were performed using EAST Version 6.4.

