### 12.4 Randomization

Subjects will be randomized in a 1:1 ratio to Gan & Lee Insulin Glargine Injection or Lantus® treatment. Subject randomization will be stratified by country.

Registration and randomization will take place using a centralized IXRS. At registration, the IXRS will assign a unique subject identification number that will be used on all of that subject's eCRFs and serious adverse event report forms.

The study is not blinded. However, to avoid the introduction of operational bias into final study results and to increase the interpretability and reliability of the data, certain roles of the Sponsor and study team will be blinded. Details will be provided in the Data Blinding and

Documentation of Aggregate Data Dissemination Plan (hereafter referred to as the Blinding Plan).

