**Table 6: Listing of hypoglycemic event summaries and analyses**

Analysis description	Section Reference	Tables Associated
1. Summary of Retrospective Continuous Glucometer Monitor (CGM): Hypoglycemia Rate	Section 11.7.3.1	Table 14.3.3.4.1
2. Retrospective Analysis of Continuous Glucometer Monitoring (CGM): Time in Hypoglycemia, Hyperglycemia and Euglycemia	Section 11.7.3.2	Table 14.3.3.4.2
3. Overall Summary of Treatment-Emergent Adverse Events	Section 11.8.1	Table 14.3.2.1
4. Treatment-Emergent Adverse Events by System Organ Class, Preferred Term	Section 11.8.1	Table 14.3.2.2
5. Hypoglycemic Treatment-Emergent Adverse Events by System Organ Class, Preferred Term, and Maximum CTCAE Grade (based on lowest blood glucose values measured by test method)	Section 11.8.2.1	Table 14.3.2.6.1
6. Severe Hypoglycemic Treatment-Emergent Adverse Events by Preferred Term	Section 11.8.1	Table 14.3.2.7
7. Serious Hypoglycemic Adverse Events by Preferred Term	Section 11.8.3	Table 14.3.2.13
8. IP-Related Serious Hypoglycemic Adverse Events by Preferred Term	Section 11.8.3	Table 14.3.2.14
9. Summary of Symptomatic or Persistent Hypoglycemic Treatment-Emergent Adverse Events	Section 11.8.2	Table 14.3.2.17
10. Summary of Symptomatic or Persistent Hypoglycemic Treatment-Emergent Adverse Events by Site	Section 11.8.2	Table 14.3.2.18
11. Analysis of Hypoglycemic Treatment-Emergent Adverse Events	Section 11.8.2	Table 14.3.2.19
12. Summary of Reported ADA Hypoglycemic Treatment-Emergent Adverse Events	Section 11.8.2.2	Table 14.3.2.20
13. Overall Summary and Analysis of Treatment-Emergent Adverse Events by ERIPD Subgroup in SS, PPS2, and PPS3	Section 11.8.1	Table 14.3.2.21; 14.3.2.22; 14.3.2.23; 14.3.2.24
14. Maximum Post-baseline Fasting Glucose CTCAE Grade	Section 11.8.4.1	Table 14.3.3.4.16

Subject incidence of the following TEAEs will be tabulated by preferred term in descending order of frequency in the total column:

- CTCAE Grade \geq 3 TEAEs
- Hypoglycemic TEAEs
- CTCAE Grade 3 or Greater Hypoglycemic AEs
- IP-related TEAEs
- CTCAE Grade \geq 3 IP-related TEAEs
- Fatal AEs
- SAEs
- IP-related SAEs
- Serious Hypoglycemic AEs
- IP-related Serious Hypoglycemic AEs
- AEs Pertaining to Injection Site Reactions

A forest plot of the difference in incidence rates and CIs of TEAEs preferred terms with a $\geq 5\%$ difference in incidence between groups will be summarized. The 90% CIs will be computed using Wald method for risk difference without continuity correction.

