Additionally, the hypoglycemic event rate will be compared between treatment groups using a negative binomial regression model (Table 6, Analysis 11). The response variable in the model will be the number of hypoglycemia events. The model will include factors for treatment group and site. Site has been included as a factor as different handling of documentation of hypoglycemia event are identified. The logarithm (to base e) of the follow-up time will be used as an offset variable in the model to adjust for subjects having different exposure times. The estimated treatment effect and the corresponding 95% CI, as well as the 2-sided p-value will be presented.

A sample SAS code fragment is provided below for reference:

```
proc genmod data = <data>;
  class trt site;
  model count = trt site / dist = negbin offset = time_log;
  lsmeans trt / ilink diff exp cl;
run;
```

All TEAEs will be listed for subjects in the SS. A listing of all TEAEs leading to discontinuation of IP will be provided.

All non-treatment-emergent AEs recorded on the CRF will be listed separately for all screened subjects.

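### With about 100 small sites as fixed effects, the negative binomial model for hypoglycemia rates gives a 95% CI about 8-10% too narrow

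*SAP*

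**What the plan says.** The model is described in the SAP just before Section 11.8.2 and is listed as Analysis 11 in SAP Table 6. It is a negative binomial regression of the number of hypoglycemia events, with log follow-up time as offset, reported with a 95% CI and a two-sided p-value. On its terms the SAP states: "The model will include factors for treatment group and site". The sample `PROC GENMOD` code lists site in the class statement and then has "model count = trt site / dist = negbin offset = time_log". It contains no random effect, repeated statement or small-sample correction. The reason for adjusting is given: "Site has been included as a factor as different handling of documentation of hypoglycemia event are identified".

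The size of the trial comes from the protocol. The Synopsis says "Approximately 100 sites are planned in the United States and Europe", and Section 12.2 says "Enrollment is planned for 550 subjects overall (275 subjects per treatment group"). Section 12.4 says "Subject randomization will be stratified by country", so the arms are not balanced within site by design. Section 11.3 explains the interest in this outcome: "In this study, hypoglycemia will be monitored as an adverse event of special interest".

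**The concern.** At the planned figures there are 550/100 = 5.5 subjects per site and about 101 fitted mean parameters (100 sites plus treatment) for 550 observations. Fitting a separate level to each small site absorbs part of the between-subject variation. Maximum likelihood then estimates the dispersion from what is left as if no parameters had been spent. The dispersion comes out too low, and the treatment standard error, CI and p-value inherit the error.

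In the visible SAP text this is the only comparison of hypoglycemia rates with a p-value. The other formal safety intervals nearby are the forest-plot risk differences for preferred terms: "The 90% CIs will be computed using Wald method for risk difference without continuity correction". An interval that is too narrow raises the chance of reporting a false difference in hypoglycemia between the biosimilar and Lantus, in either direction.

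**Working it through.** **The plan's own figure.** The documents give no event rate, dispersion or error rate for this model. The only stated figure tied to the 550 subjects is the power of the primary test, about 85% at a 30% rate and a 12% margin. It reproduces: SE = sqrt(2 × 0.3 × 0.7/275) = 0.0391, and power = 2Φ(0.12/0.0391 − 1.645) − 1 = 84.6%. It has no bearing on the hypoglycemia model.

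**Inputs from the documents.** 550 subjects, 1:1; about 100 sites planned; randomization stratified by country; 26 weeks of treatment; log follow-up offset; nominal two-sided 5%.

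**Inputs assumed.** Event rate, dispersion, between-site spread, site sizes and share with shortened follow-up. Ranges are given below.

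**Step 1: approximation.** With p mean parameters and no degrees-of-freedom correction, the ratio of reported to true SE is about sqrt((n − p)/n).
- 100 sites: sqrt((550 − 101)/550) = 0.904, so the CI is 9.6% too narrow. Rejection = 2[1 − Φ(1.96 × 0.904)] = 7.7%.
- 75 sites: 0.928, 6.9%.
- 50 sites: 0.953, 6.2%.

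At 100 sites, a reported z between 1.96 and 1.96/0.904 = 2.17 (reported p between about 0.03 and 0.05) would not be significant with a correct SE.

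**Step 2: simulation with no treatment effect.** SEs are from the observed information.
- *Set A:* 4,000 trials per scenario (Monte Carlo SE about 0.35-0.45 points). Site SD 0.6 on the log scale, unequal site sizes, 5 countries, 12% with shortened follow-up. The 100-site row uses mean 2-10 events and dispersion 1.0-1.5.
- *Set B:* 8,000 trials per scenario (Monte Carlo SE about 0.3 points), with a fitter that matched statsmodels on a test data set. The 100-site row covers mean 1-50 events, dispersion 0.5-2, site log-SD 0-1, and equal or unequal sites.

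| Sites | A: fixed site, rejection | B: fixed site, mean SE / empirical SD | B: rejection | A: random site + fixed country, rejection |
|---|---|---|---|---|
| 100 | 7.4-8.2% | 0.89-0.93 | 7.0-8.3% | 5.1-5.6% |
| 80 | 7.0% | – | – | 5.7% |
| 75 | – | 0.947 | 6.4% | – |
| 60 | 6.0-6.3% | – | – | 4.9-5.0% |
| 50 | – | 0.956 | 6.1% | – |
| 40 | 5.7-6.1% | – | – | 5.1-5.5% |
| 30 | – | 0.975 | 5.8% | – |
| 10 | 5.7% | – | – | – |
| 1 | – | 0.994 | 5.2% | – |

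At 100 sites, set A had SEs 8-10% too small and dispersion 22-36% too low. In set B the estimated dispersion was 52-85% of the true value. Further runs at 100 sites with mean 5-10 events gave SEs 7-10% too small (average about 8%) and 6.4-7.8% rejection (average about 7.1%). With expected-information SEs the error is larger: 8.3-10.3% rejection in set A and 8.2-9.6% in the further runs. The conclusion rests on the smaller, observed-information figures.

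**Step 3: alternatives at 100 sites.**
- Dropping site: 9.6% rejection in one scenario (site SD 0.7).
- Keeping fixed sites with a Pearson-moment dispersion: 7.3-9.3%.
- Random site intercept with fixed country: 5.1-5.6%, SE within 2% of the true SD, and a treatment estimate with 4-8% smaller true SD.
- Random site intercept without country: about 4.9% with normal site effects and 5.3% with non-normal ones (2,800 trials each).
- Non-normal sites (15% of sites recording at 0.15 times the rate): fixed 7.8-8.2%, random with country 5.3-5.8%.

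**The case against.** The strongest objection is that the size depends on a number nobody outside the sponsor can see. About 100 sites is a planning figure. If 40-60 enrolled, rejection is about 6%, hard to separate from set A's 10-site control at 5.7%. Measured against that control, the excess at 100 sites is about 1.7-2.5 points rather than 2.4-3.2. The supplied SAP text also has gaps, and a rule for pooling small sites could sit in one of them. All of this stands, and it makes the finding conditional.

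Second, little hangs on the result. The comparison has no margin or success criterion, and the protocol describes safety summaries as descriptive. The SAP also plans a by-site hypoglycemia summary and CGM-based summaries against which a chance finding could be checked. This limits the weight of the point, but it does not make the interval correct.

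Third, a random intercept assumes normal site effects, and most of the simulations generated them that way. Only one kind of non-normal pattern was tried; there the random-intercept model stayed within about 0.8 points of nominal. A simpler route is to multiply the fixed-site SE by sqrt(550/449) = 1.107, which would move the set B ratios of 0.89-0.93 to about 0.99-1.03. That is arithmetic on the simulated ratios and was not simulated as a procedure, and it forgoes the precision gained from a random intercept.

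**Conclusion.** The concern holds on its stated condition. If about 100 sites enrol without pooling, the planned 95% CI is about 8-10% too narrow (7-11% across all scenarios) and the nominal 5% test rejects about 7-8% of the time (6.4-8.3% across all runs). The result changes little over the assumed event rates, dispersions and site spreads; what drives it is the number of subjects per site. At 40-60 sites the error is small. The SAP's reason for adjusting for site is sound, and removing site makes matters worse, so the fault lies only in how site enters the model. This is a worthwhile correction to a supportive safety analysis. It does not touch the primary antibody or key secondary HbA1c analyses.

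**What to change.** Fit site as a random intercept: `PROC GLIMMIX` with `dist=negbin`, `method=laplace` and `random intercept / subject=site`. Keep treatment as a fixed factor and the same log follow-up offset; country, the randomization stratum, may be added as a fixed factor. Report the planned fixed-site fit as a sensitivity analysis. The count of subjects randomized per site, already planned in SAP Section 11.2, will show how much the choice matters.

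The cost is a change of SAP wording and one procedure, with no new data. The downside is the assumption of normal site effects, which cost at most about 0.8 points of type I error in the scenario with a few under-documenting sites.

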## 9.2 Visit 2: Randomization (Day 1)

At Visit 2, eligible subjects will be centrally randomized 1:1 in an open-label fashion to receive either Gan & Lee Insulin Glargine Injection or Lantus®. The following information will be collected or procedures performed:

- Concomitant medications and adverse events
- Vital signs, body weight, and BMI
- Venous blood will be collected for the following tests:
  - FBG test
  - Optional PK (blood should be collected before the subject administers the regular insulin dose)
- Urine samples will be collected for urinalysis and, for female subjects of childbearing potential, a urine pregnancy test
- Review of insulin use and glucose results since the previous visit, and the Hypoglycemic Events Record
- The CGM sensor that was applied at the screening visit will be collected (either provided by the subject in a biohazard bag, or removed from arm by the site staff if the end of the 8-day CGM period coincides with the date of the randomization visit)
- The 8-day Mealtime & Insulin Dose Record will be collected and reviewed
- Additional glucose testing supplies will be issued if needed
- IP will be issued
- The Investigator or designee will provide instruction and conduct training on all study procedures and proper dose administration

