## 11. SAFETY MEASUREMENTS AND VARIABLES

### 11.1 Adverse Events

The definitions and reporting procedures provided in this protocol comply with the current CFR 21 Part 312. An adverse event is any untoward medical occurrence or worsening of a pre-existing condition, regardless of the relationship to the investigational medicinal product. An adverse event can therefore be any unfavorable or unintended sign, including an abnormal laboratory finding, symptom or disease temporally associated with the use of an investigational medicinal product whether or not considered related to the investigational medicinal product.

Adverse events will be recorded beginning at the screening visit. Nonserious adverse events will be recorded from the time informed consent is signed through the subject's last study visit (or termination if the subject terminates early from the study for any reason). Serious adverse events will be collected from the time informed consent is signed through and including 30 calendar days after the last dose of treatment with IP.

The Investigator or designee will record all adverse events on the eCRF, regardless of the Investigator's assessment of causality, including a description of the event, severity, time of occurrence, duration, any action (e.g., treatment and follow-up tests), the event outcome, and the Investigator's assessment of the relationship to the study treatment.

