7.3 Safety

1) American Diabetes Association (ADA) Severe Hypoglycemic AE

A hypoglycemic AE will be classified as "ADA-severe" if the answer to the question "Was third party intervention required for this episode of hypoglycemia?" is Yes on the Hypoglycemia CRF page as mentioned in the ADA hypoglycemia position statement (3).

ADA Severe Hypoglycemic AE should not be confused with hypoglycemia AEs that are graded severe (Grade 3) per National Cancer Institute Common Terminology Criteria for Adverse Events (NCI CTCAE) grade (see Section 11.8.2.1).

2) Adverse Event Leading to Discontinuation of IP

An AE will be classified as an AE leading to discontinuation of IP if the answer to the question "Did the adverse event cause the subject to be discontinued from the study?" is Yes on the AE CRF page.

3) Hypoglycemic AE

An AE will be classified as a hypoglycemic AE if the answer to the question "Is this a hypoglycemic event?" is Yes on the AE CRF page.

4) Injection Site Reactions

Injection site reactions will be identified using the Medical Dictionary for Regulatory Activities (MedDRA) High Level Term = "Injection site reaction".

5) IP-related adverse events

An AE will be classified as related to IP if the relationship to study treatment is Possibly Related, Probably Related, or Definitely Related. Additionally, if the relationship is missing, then the AE will be deemed IP-related.

6) Persistent/Non-persistent Hypoglycemic AE

Hypoglycemic event with Time in hypoglycemia (see definition in Section 7.4) greater or equal to an hour (per CGM) would be classified as persistent. A hypoglycemic event with Time in hypoglycemia below an hour (per CGM) would be classified as non-persistent.

7) Symptomatic Hypoglycemic AE

A Hypoglycemic AE will be classified as symptomatic if the answer to the question "Was subject aware of symptoms?" is Yes on the Hypoglycemia CRF page.

8) Treatment-emergent adverse events

Treatment-emergent adverse event (TEAE) is an event that started or worsened in severity on or after the day of the first dose of IP but not more than 30 days after the subject's last dose of IP.

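### The hypoglycemia rate model omits each subject's pre-treatment hypoglycemia, which the trial already collects, and so may lose some precision

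*SAP*

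**What the plan says.** The model stands in SAP Section 11.8.1, just before Section 11.8.2, and is Analysis 11 in Table 6. On its terms the SAP says "The model will include factors for treatment group and site". The code agrees: "model count = trt site / dist = negbin offset = time_log". On exposure, "The logarithm (to base e) of the follow-up time will be used as an offset variable in the model". On output, "The estimated treatment effect and the corresponding 95% CI, as well as the 2-sided p-value will be presented". Site is included because sites documented hypoglycemia differently.

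Table 6 describes Analysis 11 as an analysis of treatment-emergent events. SAP Section 7.3 limits these to events that "started or worsened in severity on or after the day of the first dose of IP" (and no more than 30 days after the last dose), so screening events are not in the response.

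Pre-treatment hypoglycemia is nevertheless collected:

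- Protocol 11.1: "Adverse events will be recorded beginning at the screening visit".
- Protocol 9.1 issues the glucometer and the Hypoglycemic Events Record at screening, and Protocol 9.2 lists for Day 1 "Review of insulin use and glucose results since the previous visit, and the Hypoglycemic Events Record".
- Protocol 11.3 has the data-capture system ask for extra detail on each hypoglycemic AE.
- Protocol 8.1 and 8.6.2 have a CGM sensor worn for 8 days from screening.

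For the AE data, the SAP's stated use is a listing: "All non-treatment-emergent AEs recorded on the CRF will be listed separately for all screened subjects". For CGM, SAP Section 7.4 defines time in hypoglycemia at all three wear periods, including screening. No visible text brings either source into the rate model.

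**The concern.** Hypoglycemia is the only adverse event of special interest named in Protocol 11.3. In a comparison with a reference product, the width of the interval decides how large a rate difference can be excluded.

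A subject's own recent rate is a natural predictor of the later rate. It comes from the same subject, site and recording process as the outcome, so it can pick up differences between subjects within a site, which a site factor cannot. The SAP already does the analogous thing for HbA1c, where the ANCOVA includes the baseline value. No reason is given for treating hypoglycemia differently. If subject rates persist from screening into treatment, the present model leaves explainable variation in the standard error and chance baseline imbalance in the estimate.

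**Working it through.** **Plan figures.** The documents state no rate, dispersion, power or interval width for this model, so there is no plan figure to reproduce for it. The design size does reproduce. With n = 275 per arm, AIA rate 30% and margin 12%, TOST power = 2Φ(0.12/√(2·0.3·0.7/275) − 1.645) − 1 = 84.6%, against about 85% stated (Protocol 12.2, SAP 5.1).

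**Inputs from the documents.** 275 per arm, 1:1; 26 weeks (182 days) of treatment; screening of at most 14 days (Protocol 9.1).

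**Assumptions.** Event rate, dispersion k, and correlation ρ between a subject's log rates before and during treatment.

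**Analytic guide (upper end).** Var(log rate ratio) ≈ (2/n)(1/μ + k), where μ is the mean on-treatment count. If the subject effect is fully persistent and the baseline count has mean μ₀, k falls to about k/(1 + kμ₀). At 10 events/year and k = 1:

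- μ = 10 × 182/365.25 = 4.98, so 1/μ = 0.201
- μ₀ = 10 × 14/365.25 = 0.383, so k becomes 1/1.383 = 0.723
- width ratio = √[(0.201 + 0.723)/(0.201 + 1)] = 0.877

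The same formula gives 0.994 at 1/year, 0.941 at 5/year and 0.740 at 25/year. It has no site factor and assumes a full 14-day window and full persistence.

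**Simulation closer to the SAP model.** 550 subjects, 90 sites as fixed effects, screening of 10-14 days, about 12% early discontinuation (assumed) and a true rate ratio of 1. Maximum-likelihood negative binomial fits with and without log[(baseline count + 0.5)/baseline time]; 100 runs per setting. The median ratio of interval widths on the log scale (adjusted / SAP model) was:

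| Events/year | k | ρ | Ratio |
|---|---|---|---|
| 1 | 1 | 1 | 0.999 |
| 1 | 2 | 0.7 | 0.998 |
| 5 | 1 | 0.7 | 0.983 |
| 10 | 1 | 1 | 0.926 |
| 10 | 1 | 0.7 | 0.966 |
| 10 | 2 | 0.7 | 0.957 |
| 10 | 1 | 0.4 | 0.992 |
| 10 | 1 | 0 | 1.000 |
| 25 | 1 | 0.7 | 0.936 |
| 25 | 2 | 0.7 | 0.919 |
| 50 | 1 | 0.7 | 0.903 |
| 50 | 2 | 1 | 0.721 |

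At 10/year, k = 1, ρ = 0.7, the standard error goes from 0.082 to 0.079, and the 95% limits go from ×/÷1.175 to ×/÷1.168. The largest ratio in any single run was 1.017, at 1/year, so an uninformative covariate costs almost nothing.

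These are model-based widths. Coverage was 85-96% for the SAP model and 85-94% with the covariate, so it fell short of 95% in several settings for both models.

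**More variation between sites.** A second simulation (90 sites, k = 1, ρ = 0.7, 40% of log-rate variance between sites; 30 runs per setting) gave narrowing of 0.2%, 1.6%, 4.6% and 7.2% at 0.05, 0.2, 0.5 and 1 event/week. At ρ = 0.4 the narrowing was 0-2%.

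**The case against.** The strongest reply is that nothing here is wrong. Randomization protects the estimate, and chance imbalance is already reflected in the interval. The model is an added safety analysis with no visible margin, power target or place in a testing hierarchy, and the protocol synopsis plans only descriptive safety summaries. This stands: the point is about efficiency, not error or bias.

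The second reply is that screening is a poor baseline. It lasts at most 14 days, the basal dose is being optimized during it (Protocol 8.5.8), and subjects may be on another basal insulin before switching (Appendix 3). This also stands, and it is why partial persistence is the realistic case.

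Several stronger readings are tempting but unsupported:

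- **A large gain.** A reader might infer an 18-33% narrower interval, or the equivalent of about 49% more subjects (1/0.82² = 1.49). That needs full persistence, at least 0.5 events/week and a model without site.
- **Between-subject variation dominates.** At 10 events/year and k = 1 it is 1/1.201 = 83% of the variance. At 1 event/year, 1/μ is about 2 against k = 1, and the order reverses.
- **The only inferential hypoglycemia comparison.** The available SAP text is incomplete around the CGM and hypoglycemia sections, so this cannot be confirmed.
- **Pre-treatment data are only listed.** This is true of the AE data as far as the text shows, but not of CGM.
- **A clean count exists for every subject.** No visible text puts the subject-held Record in the database beyond the AE and Hypoglycemia pages, and SAP 11.8.2 allows for a blank Hypoglycemia page.

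**Conclusion.** The point holds as a modest gain in precision. The rate model omits a baseline value that the trial collects, and including it narrows the interval to the extent that a subject's rate persists from screening into treatment.

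The size rests on assumed rates, dispersion and correlation. It is negligible at about 1 event/year, about 2-10% at 5-50 events/year with ρ = 0.7, under 1% at 10/year with ρ = 0.4, and zero with no correlation. The 28% figure arises only at 50/year with k = 2 and full persistence. Confidence is high in the omission and the direction, and low in any single figure.

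**What to change.** In SAP Section 11.8.1, before treatment assignments are loaded (SAP 10.1 holds them back until unblinding for the final analysis):

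1. Add one covariate to the model statement: log[(hypoglycemic AEs from consent to the day before first dose + 0.5) / days in that period]. Count these events under the Hypoglycemia-page rule in SAP 11.8.2, the section to which Table 6 assigns Analysis 11, so that covariate and response are counted alike.
2. Keep site and the follow-up offset.
3. State one rule for subjects with a missing baseline.
4. Keep the present model as a supportive run.
5. Name the screening CGM event count as the covariate in a sensitivity analysis only. Leaving the choice between AE and CGM open would hand it to the analyst in an open-label trial.

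If assignments have already been loaded, report the adjusted model as a labeled sensitivity analysis instead.

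The cost is one derived variable and one model term. The covariate will be noisy, because the window is short and overlaps dose optimization, and subjects with no events will differ on it only through the length of screening.
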